### **3.4.2 Guidelines for the Management of Infusion Reactions**

In case of hypersensitivity reactions, the investigator should institute treatment measures deemed medically appropriate in accordance with current medical practice and treatment guidelines. Prophylactic premedication will not be routinely given before the first dose of Cycle 1. Prophylactic medication to prevent future infusion reactions may be considered after discussion and agreement between investigator(s) and the BMS Medical Monitor. Infusion reactions should be graded according to NCI CTCAE v4.03 guidelines and recorded in the CRF. Treatment recommendations are provided and may be modified based on local treatment standards and guidelines, as appropriate: In the case of infusion reactions during nivolumab administration, subsequent infusion times for individual subjects may be extended at the discretion of the investigator.

**For Grade 1 symptoms** (mild reaction; infusion interruption not indicated; intervention not indicated):

- Remain at bedside and monitor subject until recovery from symptoms.
- The following prophylactic premedications are recommended for future infusions: diphenhydramine 50 mg (or equivalent) and/or acetaminophen/paracetamol 325 mg to 1000 mg at least 30 minutes before additional study drug administrations.

**For Grade 2 symptoms** (moderate reaction; requires therapy or infusion interruption but responds promptly to symptomatic treatment [eg, antihistamines, nonsteroidal anti-inflammatory drugs, narcotics, corticosteroids, IV fluids]; prophylactic medications indicated for < 24 hours):

- Stop the study drug infusion, begin an IV infusion of normal saline, and treat the subject with diphenhydramine 50 mg IV (or equivalent) and/or acetaminophen/paracetamol 325 to 1000 mg; remain at bedside and monitor subject until resolution of symptoms. Corticosteroid therapy and/or bronchodilator may also be administered as appropriate.
- If infusion is interrupted, then restart the infusion at 50% of the original infusion rate when symptoms resolve; if no further complications ensue after 30 minutes, the rate may be increased to 100% of the original infusion rate. Monitor subject closely.
- If symptoms recur, then no further study drug will be administered at that visit.
- The amount of study drug infused must be recorded on the CRF.
- The following prophylactic premedications are recommended for future infusions: diphenhydramine 50 mg (or equivalent), acetaminophen/paracetamol 325 to 1000 mg, and/or corticosteroids (up to 25 mg of hydrocortisone or equivalent) should be administered at least 30 minutes before additional study drug administrations. Remain at bedside and monitor subject until recovery from symptoms.

**For Grade 3 or Grade 4 symptoms** (Grade 3: severe reaction; prolonged [ie, not rapidly responsive to symptomatic medication and/or brief interruption of infusion]; recurrence of symptoms following initial improvement; hospitalization indicated for other clinical sequelae [eg, renal impairment, pulmonary infiltrates]. Grade 4: life threatening; pressor or ventilatory support indicated):

- Immediately discontinue infusion of study drugs.
- Begin an IV infusion of normal saline and treat the subject as follows: recommend bronchodilators, epinephrine 0.2 to 1 mg of a 1:1,000 solution for subcutaneous administration, 0.3 mg of a 1:1,000 solution for intramuscular administration, or 0.1 to 0.25 mg of a 1:10,000 solution slowly for IV administration, and/or diphenhydramine 50 mg IV (or equivalent) with methylprednisolone 100 mg IV (or equivalent), as needed.
- Subject should be monitored until the investigator is comfortable that the symptoms will not recur.
- The amount of study drug infused must be recorded on the CRF.
- For Grade 3 infusion reactions that resolve within 6 hours, the following prophylactic premedications are recommended for future infusions: diphenhydramine 50 mg (or equivalent), acetaminophen/paracetamol 325 to 1000 mg, and/or corticosteroids (up to 25 mg of hydrocortisone or equivalent) should be administered at least 30 minutes before additional BMS-986148 administrations. Remain at bedside and monitor subject until recovery from symptoms.
- For a Grade 3 infusion reaction that does not resolve in 6 hours and Grade 4 infusion reactions, study drug will be permanently discontinued.
- Investigators should follow their institutional guidelines for the treatment of anaphylaxis.
- Remain at bedside and monitor subject until recovery from symptoms.
- In the case of late-occurring hypersensitivity symptoms (eg, appearance of a localized or generalized pruritus within 1 week after treatment), symptomatic treatment may be given (eg, oral antihistamine or corticosteroids).

### **3.5 Discontinuation of Subjects following any Treatment with Study Drug**

Subjects **MUST** discontinue investigational product (and noninvestigational product at the discretion of the investigator) for any of the following reasons:

- Subject's request to stop study treatment and/or participation in the study
- Any clinical AE, laboratory abnormality, or intercurrent illness which, in the opinion of the investigator, indicates that continued participation in the study is not in the best interest of the subject
- Termination of the study by BMS
- Loss of ability to freely provide consent through imprisonment or involuntarily incarceration for treatment of either a psychiatric or physical (eg, infectious disease) illness
- Inability to comply with protocol
- Discretion of the investigator

- Confirmed CR as defined by RECIST version 1.1 or Modified RECIST for malignant pleural mesothelioma (see [Appendix 4](#)) unless subject meets criteria to continue treatment with nivolumab
- Documented disease progression as defined by RECIST version 1.1 or Modified RECIST criteria for malignant pleural mesothelioma (see [Appendix 4](#)) unless subject meets criteria for treatment beyond progression ([Section 4.5](#)) (for subjects in Part 3)
- AE(s) requiring discontinuation as outlined in the Dose Modification section (See [Section 4.5.2](#))

In the case of pregnancy, the investigator must immediately notify the BMS Medical Monitor/designee of this event. In most cases, the study drug will be permanently discontinued in an appropriate manner. If the investigator determines a possible favorable benefit/risk ratio that warrants continuation of study drug, a discussion between the investigator and the BMS Medical Monitor/designee must occur.

All subjects who discontinue investigational product should comply with protocol specified follow-up procedures as outlined in [Section 5](#). The only exception to this requirement is when a subject withdraws consent for all study procedures including post-treatment study follow-up or loses the ability to consent freely (ie, is imprisoned or involuntarily incarcerated for the treatment of either a psychiatric or physical illness).

If study drug is discontinued prior to the subject's completion of the study, the reason for the discontinuation must be documented in the subject's medical records and entered on the appropriate CRF page.

### **3.6 Post-Study Drug Follow Up**

Safety is a key endpoint of this study. Post-study follow-up is of critical importance and is essential to preserving subject safety and the integrity of the study. Subjects who discontinue study drug must continue to be followed for collection of outcome and/or Survival Follow-up data as required and in line with [Section 5](#) until death or the conclusion of the study.

BMS may request that survival data be collected on all treated subjects outside of the protocol-defined window ([Table 5.1-2](#) through [Table 5.1-8](#)). At the time of this request, each subject will be contacted to determine their survival status unless the subject has withdrawn consent for all contacts or is lost to follow-up.

#### **3.6.1 Withdrawal of Consent**

Subjects who request to discontinue study drug will remain in the study and must continue to be followed for protocol specified follow-up procedures. The only exception to this is when a subject specifically withdraws consent for any further contact with him/her or persons previously authorized by subject to provide this information. Subjects should notify the investigator of the decision to withdraw consent from future follow-up **in writing**, whenever possible. The withdrawal of consent should be explained in detail in the medical records by the investigator, as to whether the withdrawal is from further treatment with study drug only or also from study procedures and/or post-treatment study follow-up, and entered on the appropriate CRF page. In the event that vital status (whether the subject is alive or dead) is being measured, publicly

available information should be used to determine vital status only as appropriately directed in accordance with local law.

### **3.6.2 Lost to Follow-Up**

All reasonable efforts must be made to locate subjects to determine and report their ongoing status. This includes follow-up with persons authorized by the subject as noted above. Lost to follow-up is defined by the inability to reach the subject after a minimum of 3 documented phone calls, faxes, or emails as well as lack of response by subject to 1 registered mail letter. All attempts should be documented in the subject's medical records. If it is determined that the subject has died, the site will use permissible local methods to obtain the date and cause of death.

If investigator's use of a third-party representative to assist in the follow-up portion of the study has been included in the subject's informed consent, then the investigator may use a Sponsor-retained third-party representative to assist site staff with obtaining subject's contact information or other public vital status data necessary to complete the follow-up portion of the study. The site staff and representative will consult publicly available sources, such as public health registries and databases, in order to obtain updated contact information. If after all attempts, the subject remains lost to follow-up, then the last known alive date as determined by the investigator should be reported and documented in the subject's medical records.

## **4 STUDY DRUG**

Study treatment includes both investigational medicinal product (IMP)/investigational product (IP) and noninvestigational medicinal product (NIMP)/non-IP and can consist of the following:

- All products being tested in a clinical trial.
- Study required premedication, and other drugs administered as part of the study that are critical to claims of efficacy (eg, background therapy, rescue medications)
- Diagnostic agents (such as glucose for glucose challenge) given as part of the protocol requirements must also be included in the dosing data collection.

Product description and storage information is described in [Table 4-1](#).

**Table 4-1: Study Drugs for CA008002**

Product Description Class and Dosage Form	Potency	IP/NIMP	Blinded or Open Label	Packaging/Appearance	Storage Conditions (per Label)
BMS-986148-01 for Injection	50 mg/vial	IP	Open	10 cc vial/White to off white, whole or fragmented cake in a vial Lyophilized	Protect from light Store at 2°C to 8°C
Nivolumab	100 mg/ vial (10 mg/mL)	IP	Open	Primary Packaging: 10 mL (10 cc) glass vial Secondary Packaging: Outer carton Appearance: Vial containing 10 mL Clear to opalescent, colorless to pale yellow liquid, light (few) particulates may be present.	2°C to 8°C (36°F - 46°F) Protect from light. Protect from freezing.

IP: investigational product; NIMP: non-investigational medicinal product.

#### **4.1 Investigational Product**

Study treatment is defined as any investigational treatment(s), marketed product(s), placebo or medical device intended to be administered to a study participant according to the study randomization or treatment allocation. An investigational product, also known as an IMP in some regions, is defined a pharmaceutical form of an active substance or placebo being tested or used as a reference in a clinical study, including products already with a marketing authorization but used or assembled (formulated or packaged) differently than the authorized form, or used for an unauthorized indication, or when used to gain further information about the authorized form.

The investigational product should be stored in a secure area according to local regulations. It is the responsibility of the investigator to ensure that investigational product is only dispensed to study subjects. The investigational product must be dispensed only from official study sites by authorized personnel according to local regulations.

#### **4.2 Noninvestigational Product**

Other medications used as support or escape medication for preventative, diagnostic, or therapeutic reasons, as components of the standard of care for a given diagnosis, may be considered noninvestigational products. Not applicable for this study.

#### **4.3 Storage and Dispensing**

The product storage manager should ensure that the study drug is stored in accordance with the environmental conditions (temperature, light, and humidity) as determined by BMS. If concerns regarding the quality or appearance of the study drug arise, the study drug should not be dispensed and BMS should be contacted immediately.

Investigational product documentation (whether supplied by BMS or not) must be maintained that includes all processes required to ensure drug is accurately administered. This includes documentation of drug storage, administration, and, as applicable, storage temperatures, reconstitution, and use of required processes (eg, required diluents, administration sets).

#### **BMS-986148 Preparation**

BMS-986148 is supplied as a sterile, nonpyrogenic, single use, preservative-free lyophilized cake with a strength of 50 mg/vial that must be reconstituted and diluted prior to dosing the subject as an IV injection formulation. A sufficient excess of BMS-986148 is incorporated into each vial to account for withdrawal losses.

Solutions for infusion are prepared by injecting a specific volume of BMS-986148 drug product and normal saline into an empty 50-cc IV infusion bag (supplied by the site) to yield appropriate solutions for infusion.

BMS-986148-01 for injection is to be administered as an IV infusion, following reconstitution with sterile water for injection, and further dilution with normal saline (0.9% w/v sodium chloride) to concentrations appropriate for the dosing cohort.

Instructions for the drug product preparation, administration, and storage are provided in the pharmacy manual.

### **BMS-986148 Administration**

The administration of the entire bag contents (or the amount needed if the total dose is less than 50 mg) should be infused within approximately 60 minutes through an IV infusion set (sterile, nonpyrogenic, low protein binding, polyethersulfone 0.2- $\mu$ m in-line filter) (supplied by the site). Care must be taken to ensure the sterility of the prepared solution, as the drug product does not contain antimicrobial preservatives or bacteriostatic agents. Equilibration to room temperature is recommended for the drug product, infusion fluid, and their combination prior to administration.

Reconstituted (with sterile water for injection) and diluted solutions (in normal saline) of BMS-986148-01 for injection are stable for up to 24 hours, at either refrigerated conditions, 2°C to 8°C (36°F to 46°F), and light protected or 4 hours at room temperature conditions, 15°C to 25°C (59°F to 77°F), under ambient light. The constituted vial and diluted bag should not be shaken. Infusion of BMS-986148-01 injection must be completed within 24 hours of dilution. The start of drug infusion equals 0 hour.

For subjects receiving nivolumab in combination with BMS-986148, subjects should receive nivolumab at a dose of 360 mg as a 30-minute infusion on Day 1 of each 21-day treatment cycle until disease progression, unacceptable toxicity, withdrawal of consent, or the study ends, whichever occurs first.

For combination treatment in Part 3, BMS-986148 will be administered as an infusion up to 60 minutes. The infusion line containing BMS 986148 should be flushed with an appropriate amount of diluent to ensure that the entire dose is administered and that the infusion line is cleared of any remaining BMS-986148. The nivolumab dose would then be infused not less than 30 minutes from the completion of the BMS-986148 infusion, which would then be infused over a period of 30 minutes.

The start and stop time of the all study therapy infusions and any interruptions or infusion rate reductions should be documented.

Refer to the IB for additional details about BMS-986148.

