**Figure 3.1-2: Dosing (Q3W and QW) and Study Periods**

Note: Subjects treated for > 2 years will be followed for 6 months after EOT in the Survival Follow-Up. Additionally, specifically in Part 3, treatment duration is 24 weeks to a maximum of 48 weeks.

C1D1: Cycle 1 Day 1 (first dose); D: day; DLT: dose-limiting toxicity; EOT: end of treatment; QW: every week; Q3W: every 3 weeks.

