### **3.1.4 Administration of Additional Treatment Cycles (Part 3)**

In Part 3 of this study, all subjects will be treated for 24 weeks (up to 8 cycles) of BMS-986148 in combination with nivolumab unless criteria for study drug discontinuation are met earlier ([Section 3.5](#)). All subjects completing approximately 24 weeks of study therapy with ongoing disease control (CR, PR, or SD) may be eligible for an additional 24 weeks of study therapy at the originally assigned dose regimen in both escalation and cohort expansion beyond the initial 24 weeks, on a case-by-case basis, after careful evaluation and discussion with the BMS Medical Monitor to determine whether the benefit/risk ratio supports administration of further study therapy. Upon completion of 24 weeks of study therapy (or up to a maximum of 48 weeks if applicable), all subjects will enter the clinical/safety Follow-up period.

Following every 2 treatment cycles (every 6 weeks [Q6W] for Part 3), the decision to treat a subject with additional cycles of study therapy will be based on radiological tumor assessments (initial evaluation performed at baseline and every 2 cycles or every 6 weeks). Treatment decisions related to subject management will be based exclusively on Response Evaluation Criteria in Solid Tumors (RECIST) version 1.1 or Modified RECIST for malignant pleural mesothelioma (see [Appendix 4](#)). Assessments of PR and CR must be confirmed at least 4 weeks following initial assessment. Subjects with an overall response of CR, PR, or SD will continue therapy until they develop CR confirmed, develop progressive disease, experience clinical deterioration, develop AEs requiring discontinuation of treatment, or withdraw consent. Individual subjects with confirmed CR will be given the option to continue BMS-986148 in combination with nivolumab on a case-by-case basis after specific consultation and agreement between the investigator and BMS Medical Monitor in settings where benefit/risk justify continuation of study therapy.

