### **3.1.7 Retreatment during Survival Follow-Up (Part 3)**

Retreatment may be allowed in Part 3 of this study with disease progression during follow-up. Subjects completing approximately 24 weeks of study therapy (or up to a maximum of 48 weeks if applicable), who enter Survival Follow-up with ongoing disease control (CR, PR, or SD) for reasons other than drug-related toxicity, may be eligible for retreatment, upon subsequent confirmed disease progression within 12 months of the last dose of study drug, on a case-by-case basis, after careful evaluation and discussion with the BMS Medical Monitor to determine whether the benefit/risk ratio supports administration of further study therapy. Subjects meeting criteria for retreatment will be treated up to an additional approximately 24 weeks with the originally assigned dose regimen (eg, same dose and dose schedule administered during the first 24 weeks) or modified dose regimen, unless that dose and schedule were subsequently found to exceed the MTD, in which case the subject will be treated at the next lower or alternate dose and schedule (see [Table 4.5.2-1](#)). Subjects entering this phase will follow the schedule as outlined in [Table 5.5.1-4](#). Samples for PK will be collected less frequently ([Table 5.5.1-4](#)).

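### Part 3: Section 4.3 puts no time limit on nivolumab, while Section 3.1.4 ends combination therapy at 24 weeks, or at most 48 with an extension

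*Protocol*

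**What the plan says.** Protocol Section 4.3, under the BMS-986148 Administration subheading, states how nivolumab is given in combination. It is infused "on Day 1 of each 21-day treatment cycle" and continues "until disease progression, unacceptable toxicity, withdrawal of consent, or the study ends, whichever occurs first". The text names no number of weeks or cycles and does not point to the section that sets the length of Part 3 treatment.

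Section 3.1.4 sets that length. In Part 3, "all subjects will be treated for 24 weeks (up to 8 cycles) of BMS-986148 in combination with nivolumab", unless a discontinuation criterion is met sooner. Subjects who reach about week 24 with a response or stable disease "may be eligible for an additional 24 weeks of study therapy at the originally assigned dose regimen", decided individually after discussion with the sponsor's medical monitor. The section then closes the course: "Upon completion of 24 weeks of study therapy (or up to a maximum of 48 weeks if applicable), all subjects will enter the clinical/safety Follow-up". The synopsis repeats the rule, and the notes under synopsis Figure 2 and Figure 3.1-2 both say that "specifically in Part 3, treatment duration is 24 weeks to a maximum of 48 weeks".

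Two further provisions matter. Section 3.1.4 also contains a sentence that does not restate the limit: "Subjects with an overall response of CR, PR, or SD will continue therapy until they develop CR confirmed, develop progressive disease", or meet one of several other stopping events. Section 3.1.7 provides a separate, later course for subjects who progress after leaving treatment with disease control: "Subjects meeting criteria for retreatment will be treated up to an additional approximately 24 weeks".

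**The concern.** Section 4.3 reads as a complete stopping rule: it lists the events that end nivolumab, includes study end among them, and says the first to occur governs. Elapsed treatment time is not on the list. A site working from it would go on giving nivolumab to a subject whom Section 3.1.4 sends to Follow-up.

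The last dose is an anchor for several outcomes. Adverse events, the primary endpoint, are evaluated to 100 days after the last dose of combination therapy (Section 8.3.1). Section 3.1.7 admits to retreatment only subjects who completed the limited course and left it with disease control. Tumor assessments change from a cycle-based schedule to a follow-up schedule when treatment ends (Table 5.1-7). If sites follow different passages, subjects with the same clinical course would differ in exposure, in the period over which their adverse events count, and in how closely later progression is dated.

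**Working it through.** **Cycle counts.** Cycles = weeks × 7 / 21. For 24 weeks, 24 × 7 / 21 = 8, which reproduces the figure in Section 3.1.4. For 48 weeks, 48 × 7 / 21 = 16.

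**The rules side by side**, for a subject with no progression, no treatment-ending toxicity and consent in place:

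| Point reached | Section 3.1.4, synopsis, figure notes | Section 4.3 (nivolumab) | Conflict |
|---|---|---|---|
| Week 24, extension not granted | Stops after cycle 8 | Cycle 9 given | Yes |
| Week 24, extension granted | Continues | Continues | No |
| Week 48 | Stops after cycle 16 | Cycle 17 given | Yes |

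Applying each passage only to the drug it names does not help. It would leave nivolumab running alone past the limit, whereas Section 3.1.4 moves every subject to Follow-up.

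**Does other text settle it?**
- Section 3.5 lists the reasons for mandatory discontinuation. Reaching 24 or 48 weeks is not among them.
- Section 4.5.2 has subjects continue until progression, a discontinuation criterion or an adverse event needing dose modification, again with no time limit.
- Table 5.1-7, the Part 3 schedule, provides in footnote b for subjects treated for more than 2 years. The longest treatment under the limit is 48 weeks plus about 24 weeks of retreatment: 48 + 24 = 72 weeks, against 104 weeks in 2 years.
- The SAP's study design (Section 2.1) covers Parts 1 and 2 only, so it offers no tie-break.

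**Adverse event window**, assuming no dose delays. The last dose of n cycles falls (n − 1) × 21 days after the first.
- 8 cycles: 7 × 21 = 147 days; the window closes at 147 + 100 = 247 days.
- 16 cycles: 15 × 21 = 315 days; the window closes at 315 + 100 = 415 days.
- Section 4.3: no fixed day; it depends on when a stopping event occurs.

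**Scans**, for a subject who stops after cycle 8, again without delays. On treatment, scans fall at the start of cycle 3 and every 2 cycles after that, so every 42 days: days 42, 84, 126, 168, 210, 252 and so on after first dose. After stopping, Table 5.1-7 has scans at end of treatment, then 60 and 100 days after the last dose (147 + 60 = 207; 147 + 100 = 247), then every 3 to 4 months. Days 207 and 247 lie close to 210 and 252. Scan timing therefore differs little up to about week 35 (247 / 7 = 35.3). Beyond that the interval is 3 to 4 months under one rule and 6 weeks under the other.

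**Retreatment.** Section 3.1.7 requires completion of about 24 weeks (or up to 48), entry to Survival Follow-up with disease control, and then confirmed progression within 12 months of the last dose. A subject kept on nivolumab until progression does not arrive by that route.

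**The case against.** The strongest reply is that the passages can be read together. Section 4.3 concerns storage, preparation and infusion; its nivolumab sentence refers to treatment cycles, and Section 3.1.4 is the dedicated section on how many cycles Part 3 has. The events in Section 4.3 would then be reasons to stop before those cycles are used up. Section 3.1.4 itself uses the same construction, setting the limit and then describing continuation until certain events without repeating it. The limit appears in four places, Section 3.1.7 depends on it, and going past week 24 requires discussion with the medical monitor, so sites are less likely to diverge unnoticed.

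Much of this stands. The limited duration is the more often stated rule, and many sites may well follow it. But the reading is not secure: a list that ends with study end, first event governing, is the form of a full stopping rule, and the discontinuation list, the continuation rule in Section 4.5.2 and footnote b of Table 5.1-7 do not carry the limit. Footnote b has the same wording as in the monotherapy schedules and may simply have been carried over, so it shows inconsistency rather than an intention to treat longer.

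A reader might also infer that every Part 3 subject in disease control at week 24 is affected. The documents do not support that: a subject granted the extension continues under both rules. Nor does the planned Part 3 total of about 137 to 162 count those affected.

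**Conclusion.** The inconsistency is real and limited. It concerns nivolumab in Part 3 subjects who are progression-free and tolerating treatment, from cycle 9 where no extension is granted and from cycle 17 otherwise. The documents give neither the share in disease control at those points nor the share granted an extension, so the number affected cannot be stated.

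It would go too far to say that Section 4.3 also contradicts the duration of BMS-986148: its open-ended sentence names nivolumab only. It would also go too far to say that endpoints become undefined. The safety window stays tied to the last dose and the PFS and response-duration definitions in Section 8.3.2.2 stand; what varies is the last-dose date and hence the exposure behind those results. A PFS rate at week 36, one of the protocol's examples, could reflect different exposure after week 24, but for a subject stopping after cycle 8 the scan timing up to then is nearly the same. Progression and response duration beyond about week 35 are where the longer scan interval matters.

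The mTPI rules and the Simon two-stage operating characteristics do not depend on this. The day counts assume 21-day cycles without delay.

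**What to change.** State one Part 3 treatment-duration rule and use it throughout. The sponsor decides which. The nivolumab sentence in Section 4.3 must be reconciled with Section 3.1.4, the synopsis text and the notes to synopsis Figure 2 and Figure 3.1-2. The sentence in Section 3.1.4 on continuing therapy until progression or another event should say how it relates to the limit. Section 3.5, Section 4.5.2 and footnote b of Table 5.1-7 should be checked against the chosen rule. Editing Section 4.3 alone would not produce a single rule.

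The cost is wording in several places in one protocol amendment. Sample size, decision rules and endpoint definitions do not change.
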